1.1.4 Licogliflozin

Licogliflozin is a selective and potent inhibitor of the sodium glucose co-transporters (SGLTs) 1 and 2 that decreases absorption of glucose in the gut and reabsorption in the kidney (Chao and Henry 2010). In the normal state, 90% of the filtered glucose is reabsorbed by SGLT2 in the proximal convoluted tubule cells of the kidney, with the remaining 10% reabsorbed by the SGLT1. Inhibition of SGLT2 results in glucosuria, decreased blood glucose and modest weight loss in healthy participants and participants with T2DM (Bays 2013). In addition to expression in the kidney, SGLT1 is also expressed in the small intestine where it is required for glucose and galactose absorption. Thus, inhibition of enteric SGLT1 results in reduction of glucose and galactose absorption (Turk et al 1991) which results in calorie wasting and other potential endocrine-based weight loss mechanisms. Combined SGLT1 and SGLT2 inhibition therefore offers the potential for improved efficacy over SGLT2 selective inhibitors in both lowering blood glucose and body weight.

Licogliflozin was administered to 76 healthy participants in the US, 36 healthy participants in Japan. Single doses of up to 350 mg and repeated doses of up to 300 mg/day for 14 days in healthy participants were generally safe and tolerated. Licogliflozin was also administered to 41 participants with T2DM and 127 obese participants in the US.

In study CLIK066X2101, single and multiple doses of licogliflozin induced glucosuria in healthy volunteers (HVs) and participants with T2DM, and significantly lowered glucose area under the time-concentration curve (AUC) after an oral glucose tolerance test (OGTT) in participants with T2DM. Licogliflozin was found to be tolerated, had in both healthy participants and participants with T2DM.

Treatment of normoglycemic and dysglycemic obese participants with 150 mg qd licogliflozin for 12 weeks in CLIK066X2201 was shown to be safe, and resulted in 5.7% reduction in body weight. Diarrhea was observed as a potential dose-limiting side effect in this study (He et al 2019). These studies are summarized in the LIK066 IB.

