8.4.2.5 Urinalysis

A clean-catch midstream urine sample will be obtained, in order to avoid contamination with epithelial cells and sediments, and allow proper assessments, as indicated in Table 8-1.

Parameters to be evaluated by urine dipstick test will include color, clarity, specific gravity, pH, glucose, protein, bilirubin, ketones, nitrite, leukocyte esterase, urobilinogen and blood. Standard microscopic evaluation of urinary sediments will be performed if the urine dipstick test shows abnormalities.

Microscopic Panel (Red Blood Cells, White Blood Cells, Casts, Crystals, Bacteria, Epithelial cells).

Urine for calculation of protein to creatinine ratio (PCR) or albumin to creatinine ratio (ACR) can be aliquoted from the clean-catch. (see Table 16-3).

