10.2.2 Renal safety monitoring

Once a participant is exposed to study treatment, renal serum and urine laboratory values will be assessed routinely. Renal laboratory triggers and renal events are defined in Table 16-3 in Section 16.3. These laboratory abnormalities should be followed up as indicated in Table 16-3 by the investigator or designated personnel at the trial site.

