16.3 Appendix 3: Specific Renal Alert Criteria and Actions and Event Follow-up

Table 16-3 Specific Renal Alert Criteria and Actions

Serum Event		
Serum creatinine increase 25 – 49% compared	Confirm 25% increase after 24-48h	
to baseline	Follow up within 2-5 days	
Acute Kidney Injury: Serum creatinine	Follow up within 24-48h if possible	
increase \geq 50% compared to baseline	Consider study treatment interruption	
	Consider participants hospitalization /specialized	
	treatment	
GFR is <60 ml x min1 x 1.73 m2	Follow up within 24-48h if possible	
	Consider study treatment interruption	
GFR is <30 ml x min1 x 1.73 m2	Follow up within 24-48h if possible	
	Consider study treatment interruption	
Urine Event	•	
Albumin- or Protein-creatinine ratio increase ≥ 2-		
fold (2 x baseline)	Confirm value after 24-48h	
Albumin-creatinine ratio (ACR) \ge 30 mg/g or \ge 3	Perform urine microscopy	
mg/mmol; Protein-creatinine ratio (PCR) ≥ 1g/g or ≥	Consider study treatment interruption / or	
100mg/mmol	discontinuation	
New onset dipstick proteinuria (≥ 3+)	Confirm assessment within 24-48 hours	
	Consider causes and possible interventions	
	Assess serum albumin & serum total protein	
	Consider drug interruption or discontinuation	
	unless other causes are diagnosed and corrected	
New onset dipstick hematuria (≥ 3+), (after	Confirm assessment within 24-48 hours	
excluding menstruation, urinary infection,	Urine sediment microscopy	
extreme exercise, or trauma)	Perform serum creatinine, ACR	
For all renal events:		
Document contributing factors in the eCRF: co-me	edication, other co-morbid conditions, and	
additional diagnostic procedures performed		
Monitor participant regularly (frequency at investig	ator's discretion) until either:	
Event resolution:		
sCr within 10% of baseline		
• protein-creatinine ratio within 50% of baseline,		
• albumin-creatinine ratio within 50% of baseline		
Event stabilization:		
• sCr level with ± 10% variability over last 6 mon	ths	
• protein-creatinine ratio stabilization at a new le	vel with \pm 50% variability over last 6 months	
• albumin-creatinine ratio stabilization at a new l	evel with ± 50% variability over last 6 months.	

Novartis Amended Protocol Version 02 (Clean)	Confidential	Page 158 of 160 Protocol No. CLJN452D12201C

Novartis Amended Protocol Version 02 (Clean)	Confidential	Page 159 of 160 Protocol No. CLJN452D12201C

Novartis

Amended Protocol Version 02 (Clean)

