#### 2.8.3 Laboratory data

Summary statistics of values and changes from baseline will be provided by visit (AV2) and by study treatment for laboratory tests listed in Table 2-6. Change from baseline will be summarized for patients with both baseline and post baseline values.

laboratory test group	Parameters	
Hematology	Hemoglobin (Hb), Hematocrit (Hct), Red blood cells (RBC), Mean corpuscular volume (MCV), Platelets, White blood cells (WBC), absolute WBC differential counts ((Neutrophils, Lymphocytes, Monocytes, Eosinophils, Basophils separately)	
General Clinical Chemistry	Sodium, potassium, chloride, bicarbonate, calcium, magnesium, phosphorus, uric acid, haptoglobin	
Liver	ALT, AST, ALP, GGT, creatine kinase (CK), lactate dehydrogenase (LDH), total bilirubin, albumin, total protein	
Renal	BUN, creatinine, estimated glomerular filtration rate (eGFR)	
Urinalysis	Albumin-creatinine ratio (ACR), Protein-creatinine ratio (PCR)	
Coagulation	INR, APTT, Prothrombin Time (PT) and Thrombin Time (TT)	
Lipids and vascular risk	Total cholesterol, HDL-C, LDL-C, VLDL-C, triglycerides, free glycerol and free fatty acids, ApoAI, high sensitivity C-reactive protein (hsCRP)	

 Table 2-6
 Laboratory safety endpoints

Shift tables for normal / abnormal (low and high based on the low/normal/high classifications from central lab) from baseline to the most extreme post-baseline value will be provided.

Number (%) of patients with post-treatment changes in laboratory criteria related to hepatotoxicity or nephrotoxicity criteria (Section 5.3.1) will also be summarized by criteria and by study treatment. In addition, patients meeting a criterion for hepatotoxicity, nephrotoxicity or other notable abnormalities defined in Section 5.3.1 will be listed, including the criteria met as well as the laboratory test name, date (study day) of lab sampling, results and units for that test and related lab tests throughout the study.

Novartis	For business use only	Page 28
SAP		CLJN452D12201C

For summaries of shift, hepatotoxicity/nephrotoxicity events or other notable laboratory abnormalities outlined above, all post-treatment data will be used regardless of last dose date.

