#### 5.3 Derivations

#### 5.3.1 Laboratory parameters

Laboratory criteria of potential hepatotoxicity for liver safety monitoring in protocol section 10.2.1 (not including additional non-lab criteria):

- ALT or AST  $> 5 \times ULN$ 

- $ALP > 2 \times ULN$
- TBL >  $2 \times ULN$
- ALT or AST  $> 3 \times$  ULN and INR > 1.5
- ALT or AST > 3  $\times$  ULN and TBL > 2  $\times$  ULN AND ALP to  $\leq$  2  $\times$  ULN (Potential Hy's Law cases)
- ALT or AST  $> 3 \times ULN$

Laboratory criteria of potential nephrotoxicity for renal safety monitoring in protocol section 10.2.2:

- Two or more consecutive serum creatinine increase  $\geq 25\%$  compared with baseline
- serum creatinine increase  $\geq 50\%$  compared with baseline
- $eGFR < 60 \text{ mL/(min*1.73m^2)}$
- Two or more consecutive albumin- or protein-creatinine ratio increase  $\geq$  2-fold
- Two or more consecutive albumin-creatinine ratio (ACR)  $\geq$  30 mg/g;
- Two or more consecutive protein-creatinine ratio (PCR)  $\geq$  150 mg/g
- Dipstick glycosuria  $\geq 1+$  for patients with negative reading at baseline
- Dipstick hematuria ≥ 1+ not due to trauma for patients with negative reading at baseline

Criteria for other notable laboratory abnormality:

Parameter	Threshold value	Unit	
Albumin	<32	g/L	
Hemoglobin	<70	g/L	
Hemoglobin	>200	g/L	
White blood cell count	<2.0	10  /L	
White blood cell count	>35.0	10  /L	
Platelets	<50	10  /L	
Platelets	>1000	10  /L	
INR	>4.0		
PT	>40.0	sec	
APTT	>80.0	sec	
Sodium	<120	mmol/L	
Sodium	>160	mmol/L	
Potassium	<3.0	mmol/L	
Potassium	>6.0	mmol/L	
Glucose	<2.2	mmol/L	
Glucose	>27.8	mmol/L	
Calcium	<1.50	mmol/L	
Calcium	>3.00	mmol/L	
Phosphate	<0.29	mmol/L	
Creatinine	>177	µmol/L	

**Table 5-1**Notable criteria for other laboratory parameters

Novartis SAP	For business use only	CLJN452E	Page 39 012201C
Calculated eGFR	<60	mL/min	

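### SAP 5.3.1 counts new dipstick glycosuria as potential nephrotoxicity, although glucosuria is the expected drug effect of licogliflozin

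*SAP*

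**What the plan says.** SAP 5.3.1 gives eight laboratory criteria of potential nephrotoxicity, described as being "for renal safety monitoring in protocol section 10.2.2". The seventh is "Dipstick glycosuria" of 1+ or more "for patients with negative reading at baseline". The smaller creatinine rise (25%) and all the albumin- and protein-creatinine ratio criteria need at least two consecutive results. The glycosuria criterion needs one, and it makes no distinction between arms.

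SAP 2.8.3 reports the number and percentage of patients with "post-treatment changes in laboratory criteria related to hepatotoxicity or nephrotoxicity criteria", with one count per criterion and per treatment. It also lists every patient who meets a criterion, and it uses all data after the start of treatment regardless of the last dose date.

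Protocol 1.1.4 states: "Inhibition of SGLT2 results in glucosuria, decreased blood glucose and modest weight loss". It adds that licogliflozin itself produced glucosuria in healthy volunteers and in participants with type 2 diabetes. Protocol 1.1.8 calls dose-dependent glucosuria expected in the animal studies, and protocol 10.2.3.4 attributes genital infections on licogliflozin to it.

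Glucose is on the dipstick panel (protocol 8.4.2.5: "Parameters to be evaluated by urine dipstick test will include color, clarity, specific gravity, pH, glucose, protein"). In the current protocol, section 10.2.2 says "Renal laboratory triggers and renal events are defined in Table 16-3 in Section 16.3". The dipstick triggers in that table are proteinuria and "New onset dipstick hematuria", each at 3+ or more. Glycosuria is not in it.

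**The concern.** A nephrotoxicity criterion is useful in a comparative safety table only if meeting it suggests kidney injury. In the two licogliflozin arms a new positive glucose dipstick is what the drug is meant to produce, so the criterion cannot separate drug action from harm there. The other arms have no such mechanism. A between-arm difference in this row is therefore built in, under a heading that invites a safety reading.

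This matters because renal safety is a real question for these drugs. Protocol 1.1.8 names the kidney among licogliflozin's target organs in animals, and protocol 1.1.7 describes renal tubular findings in rats given tropifexor. The summary and listing should be ones that a reader can take at face value. A listing filled with participants who show only the expected drug effect is harder to search for the few who may have a kidney problem.

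**Working it through.** The plan states no expected rate for this criterion, so there is no figure to reproduce. The check covers who is exposed, how easily the criterion is met, and what range of counts follows.

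**Exposure.** Current protocol (section 6.1.3): 380 allocated 1.75:1:1:1 gives 380 × 1.75/4.75 = 140 and 380 × 1/4.75 = 80 in each other arm. Licogliflozin is in Arms A and C: 140 + 80 = 220 of 380. SAP design (section 1.1): 210/3 = 70 per arm, with licogliflozin in two of three arms: 70 + 70 = 140 of 210.

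**Ease of meeting the criterion.** Protocol Table 8-1 schedules central urinalysis at ten post-baseline treatment visits (Weeks 2, 4, 8, 12, 16, 20, 24, 32, 40, 48) and at Week 52. With a per-visit chance p of a 1+ reading, and visits treated as independent for illustration only, the chance of at least one flag over ten visits is 1 − (1 − p)^10:

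| p per visit | Chance of at least one flag |
|---|---|
| 6.7% | 50% |
| 10% | 65% |
| 20% | 89% |
| 50% | 99.9% |

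Readings within a person are correlated, so these are not predictions. They show that a one-reading rule over many visits is easily met.

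**Range of counts.** Let b be the share negative at baseline and q the share of those who convert at least once. The flagged share is b × q. The documents give neither b nor q at 30 mg, so both are assumptions.

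| b | q | b × q | of 220 | of 140 |
|---|---|---|---|---|
| 0.5 | 0.5 | 0.25 | 55 | 35 |
| 0.5 | 0.9 | 0.45 | 99 | 63 |
| 0.6 | 0.9 | 0.54 | 119 | 76 |
| 0.8 | 0.9 | 0.72 | 158 | 101 |
| 0.9 | 0.9 | 0.81 | 178 | 113 |

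More than half are flagged only when b × q exceeds 0.5. With q = 0.9 this needs b above 0.5/0.9 = 0.556. These are totals flagged. The excess over the other arms is smaller by whatever background conversion occurs there, which the documents also do not give.

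**Where the flag appears.**

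| Output | Glycosuria included? |
|---|---|
| SAP 2.8.3 summary, glycosuria row | Yes |
| SAP 2.8.3 summary, the other seven rows | No |
| SAP 2.8.3 patient listing | Yes |
| SAP 2.8.1.1 renal safety events (follows protocol 16.3) | No |

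**The case against.** The strongest reply is that little is distorted. The label says potential, glycosuria has its own row, and a reader who knows the drug class will discount it. The renal safety event count in SAP 2.8.1.1 follows protocol 16.3 and already leaves glycosuria out. All of this stands, and it limits the point to one row and the listing.

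A second reply is that the SAP is dated 09-Dec-2019 and predates the placebo arm. That does not dispose of the point: the SAP's own three-arm design already gave licogliflozin in two arms, so the line did not fit that design either.

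The version gap does rule out one inference. A reader might conclude that the SAP misquotes protocol 10.2.2. The amendment log shows that Amendment 01 took laboratory details out of 10.2.2 and updated Table 16-3. The text the SAP was written against is not available, so a comparison with the 2021 protocol cannot show a wrong citation.

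Three other stronger readings are tempting and are not supported:

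- That real creatinine or protein signals would be buried in a pooled total. SAP 2.8.3 counts each criterion separately and specifies no any-criterion total.
- That most licogliflozin participants would be flagged. No baseline-negative share or conversion rate is given, and patients already positive at baseline cannot meet the criterion.
- That visible urine glucose results would unblind sites. Protocol 8.4.2 leaves central-laboratory reporting to a manual that is not among the documents, so this cannot be judged either way.

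**Conclusion.** The point holds in a limited form. SAP 5.3.1 classes an expected pharmacological effect of licogliflozin as potential nephrotoxicity, on one unconfirmed reading and without exempting the arms that receive the drug. The consequence is a mechanism-driven excess in the glycosuria row and in the patient listing of SAP 2.8.3.

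Its size is not in the documents. Under the stated assumption that baseline negativity and conversion each lie between 50% and 90%, 25-81% of licogliflozin participants would be flagged: 55-178 of 220 in the current protocol, or 35-113 of 140 in the SAP's design. Even the low end is a visible imbalance.

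The effect is confined to descriptive safety output. The creatinine, eGFR, albumin- and protein-creatinine ratio and hematuria rows, the renal event count, the efficacy analyses and the type I error rate are untouched.

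**What to change.** Remove the glycosuria line from the nephrotoxicity criteria in SAP 5.3.1. If urine glucose is summarised, put it in a separate urinalysis table labelled as a pharmacodynamic finding. The count from this criterion then falls to zero in every arm and the other seven criteria stay as they are.

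SAP 1.1 provides for amendment after a protocol change. In that update, reconcile the rest of the list with protocol Table 16-3. The two differ on dipstick hematuria (1+ in the SAP, 3+ in the table) and protein-creatinine ratio (150 mg/g against 1 g/g), and dipstick proteinuria is in the table but not in the SAP. Copying Table 16-3 across wholesale would change those thresholds as a side effect, so each difference needs a stated decision. The documents do not show which value is intended, and this point does not presume one.

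The cost is SAP wording and the matching table and listing specifications. No data collection or trial procedure changes. It is best done before unblinding.

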#### 5.3.7 T2DM status

The T2DM status at baseline is determined as follows: T2DM = Yes if:

- Type 2 diabetes mellitus is reported in Medical History OR
- Baseline fasting plasma glucose (FPG) >= 7.0 mmol/L (126 mg/dL)

Otherwise T2DM = No.

#### 5.3.8 Total NAS score

NAS score is calculated as the sum of scores of steatosis (0-3), lobular inflammation (0-3) and hepatocyte ballooning (0-2).

# 5.3.10 Vital signs

			0
Vital signs		Notable abr	normalities
		Absolute	Relative to baseline
Pulse rate (beats/min)		> 130	$\ge$ 120 and increase from baseline $\ge$ 15
		< 40	≤ 50 and decrease from baseline ≥ 15
Blood pressure (mmHg)	Systolic	> 200	$\ge$ 180 and increase from baseline $\ge$ 20
		<75	$\leq$ 90 and decrease from baseline $\geq$ 20
	Diastolic	> 115	$\ge$ 105 and increase from baseline $\ge$ 15
		< 40	$\leq$ 50 and decrease from baseline $\geq$ 15

Table 5-2Notable abnormalities in vital signs

# 5.3.11 Definitions for biopsy based endpoints

Assessment of fibrosis staging and NAFLD Activity Scores (NAS) including specifically steatosis, lobular inflammation and hepatocyte ballooning will be performed by pathological Central Reader(s).

#### 5.3.11.1 Improvement of fibrosis compared to baseline

The determination of fibrosis improvement will be based on NASH CRN staging. Only main stages (0, 1, 2, 3, 4) will be considered. For example, a change from 1c to 1b or 1a will not be counted as a one point change.

Baseline	Week 48	1 point improvement	2 point improvement		
2	0	Yes	Yes		
2	1	Yes	No		
2	≥2	No	No		
3	≤1	Yes	Yes		
3	2	Yes	No		
3	≥3	No	No		

**Table 5-3**Fibrosis stages and possible outcomes

#### 5.3.11.2 Worsening of NASH

Worsening of NASH in primary estimand is defined as meeting one of the two criteria below.

- Any increase in lobular inflammation score

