12.4.1 Definition of primary endpoint(s)/estimand(s)

Section 2.1 describes the primary estimands that contain the primary endpoints. This section defines the primary endpoints in detail.

The study uses two primary endpoints.

The first primary endpoint is: Whether (yes or no) the participant achieves improvement in fibrosis by at least one stage without worsening of NASH at week 48 compared with baseline.

One stage fibrosis improvement is defined as the decrease by one point on the NASH CRN fibrosis score, i.e. "from 3 to 2" or "from 2 to 1" (considering that the randomized participants either has stage 2 or stage 3 fibrosis at baseline). Worsening of NASH is determined if any of three components of the NAS score (Steatosis, Lobular inflammation or Hepatocyte ballooning) at Week 48 is greater than that at baseline (FDA definition).

The second primary endpoint is: Whether (yes or no) the participant has resolution of NASH and no worsening of fibrosis at week 48 compared with baseline.

[figure not shown]
Resolution of NASH is satisfied if the NAS score for lobular inflammation ≤ 1 AND the NAS score for Hepatocyte ballooning = 0, regardless of the value for steatosis (FDA definition). Worsening of fibrosis is defined as an increase in the NASH CRN fibrosis score from baseline to Week 48, i.e. "from 2 to 3", "from 2 to 4", or "from 3 to 4".

The two binary primary endpoints will be summarized as odds ratios for pairwise comparisons between treatments.

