#### 1.2 Study objectives and endpoints

#### Table 1-1 Objectives and related endpoints

-			
Objective(s)	Endpoint(s)		
Primary objective(s)	Endpoint(s) for primary objective(s)		
• To demonstrate the efficacy of tropifexor + licogliflozin as assessed by histologic improvement after 48 weeks of combination treatment compared to each monotherapy treatment in patients with NASH and stage 2 or 3 fibrosis.	Proportion of patients with resolution of NASH and no worsening of fibrosis OR improvement in fibrosis by at least one stage without worsening of NASH (no worsening of hepatocellular ballooning or lobular inflammation) at Week 48 compared with baseline. The criteria for resolution of NASH (absence of ballooning with no or minimal inflammation by histology) and other changes in histologic endpoints are further detailed in Section 5.3.11 .		
Secondary objective(s)	Endpoint(s) for secondary objective(s)		

 
Improvement in fibrosis by at least one stage with no worsening of NASH after 48 weeks of treatment
 
	• Key secondary endpoint: Proportion of patients who have at least one stage improvement in fibrosis without worsening of NASH (no worsening of hepatocellular ballooning or lobular inflammation) at Week 48 compared with baseline		

Objective(s)	Endpoint(s)

 
Resolution of NASH with no worsening of fibrosis after 48 weeks of treatment
 
	
 
Key secondary endpoint: Proportion of patients with resolution of NASH and no worsening of fibrosis at Week 48 compared with baseline
 

 
Improvement in fibrosis by at least one stage
 
	
 
Proportion of patients who have at least one stage improvement in fibrosis at Week 48 compared with baseline
 

 
Improvement in fibrosis by at least two stages with no worsening of NASH after 48 weeks of treatment
 
	
 
Proportion of patients who have at least two stage improvement in fibrosis without worsening of NASH (no worsening of hepatocellular ballooning or lobular inflammation) at Week 48 compared with baseline
 

 
Reduction in body weight from baseline after 48 weeks of treatment
 
	
 
Proportion of patients with 5% or more reduction in body weight at Week 48 compared to baseline
 

 
Change in liver fat content after 48 weeks of treatment
 
	
 
Change in liver fat content based on MRI - PDFF over time up to Week 48 compared with baseline
 

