# 2.6.1 Key secondary endpoints

Table 2-4	Key secondary endpoints and methods of analysis
-----------	---

Endpoints	Analysis method
Key secondary endpoint: Proportion of patients achieving at least one point improvement of fibrosis stage without worsening of NASH (no worsening of hepatocellular ballooning or lobular inflammation) at Week 48 compared with baseline	Same logistic regression model as used in the primary analysis for each step of hierarchical test
Key secondary endpoint: Proportion of patients achieving resolution of NASH without worsening of fibrosis stage at Week 48 compared with baseline	Same logistic regression model as used in the primary analysis for each step of hierarchical test

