#### - Any increase in hepatocyte ballooning score

#### 5.3.11.3 Resolution of NASH

Resolution of NASH in primary estimand is defined as meeting both criteria below.

- Lobular inflammation score  $\leq 1$
- Hepatocyte ballooning = 0

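### The SAP's definition of worsening of NASH leaves out steatosis, which the amended protocol counts, so the same biopsies can be classed differently on the first primary endpoint

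*SAP*

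**What the plan says.** Protocol 12.4.1 sets out the first primary endpoint as "improvement in fibrosis by at least one stage without worsening of NASH at week 48 compared with baseline" and then defines the second half of it: "Worsening of NASH is determined if any of three components of the NAS score (Steatosis, Lobular inflammation or Hepatocyte ballooning") is higher at Week 48 than at baseline. It labels this the FDA definition.

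SAP 5.3.11.2 reads: "Worsening of NASH in primary estimand is defined as meeting one of the two criteria below". The two criteria are "Any increase in lobular inflammation score" and "Any increase in hepatocyte ballooning score". Steatosis is not listed.

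The two-component wording recurs in SAP 1.2 (Table 1-1), 2.5, 2.5.1, 2.6.1 (Table 2-4), 2.6.2 and 2.7.1 (Table 2-5). In Table 1-1, for example, the endpoint is "at least one stage improvement in fibrosis without worsening of NASH (no worsening of hepatocellular ballooning or lobular inflammation").

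Three facts give the context:

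- The SAP's document history shows one version, dated 09-Dec-2019, before the first patient's first visit. SAP 1.1 describes three arms, 210 patients and no placebo.
- The rationale for Amendment 02 (30-Apr-2021) says the definition of no worsening was corrected, and that the SAP will hold the details.
- SAP 1.1 allows for an update after a protocol amendment but does not require one. SAP Section 4, which lists changes from the protocol, does not mention this definition.

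**The concern.** The SAP exists to turn protocol Section 12 into derivations. If 5.3.11.2 were programmed as it stands, some participants would be counted as responders who are non-responders under the protocol.

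The definition enters three protocol endpoints: the first primary endpoint, the key secondary composite and the two-stage fibrosis endpoint. The trial is declared successful if either combination-versus-placebo test passes (protocol 12.4.2), so one of its two routes to success depends on this rule.

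A choice between the two rules made after unblinding could not be shown to be independent of the results.

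**Working it through.** **1. The two rules side by side**

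| Component higher at Week 48 | Protocol 12.4.1 | SAP 5.3.11.2 |
|---|---|---|
| Lobular inflammation | worsening | worsening |
| Ballooning | worsening | worsening |
| Steatosis only | worsening | not worsening |

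Example: fibrosis 3 to 2, steatosis 1 to 2, inflammation 2 to 2, ballooning 1 to 1. Baseline NAS is 1 + 2 + 1 = 4, so the participant is eligible. The SAP rule gives a responder and the protocol rule a non-responder. Ballooning has not cleared, so NASH is not resolved and the composite changes too.

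**2. Direction of disagreement**

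Inputs: score ranges 0-3, 0-3 and 0-2 (SAP 5.3.8); eligibility NAS of 4 or more with inflammation and ballooning each at least 1 (protocol 5.1). Let s, l, b be baseline steatosis, inflammation and ballooning. For each baseline there are 4 x 4 x 3 = 48 Week 48 score sets. The SAP rule passes 4(l+1)(b+1) of them. Of those, the protocol rule fails (3-s)(l+1)(b+1).

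| (l, b) | Eligible s | SAP: no worsening | Of these, protocol: worsening |
|---|---|---|---|
| (1,1) | 2-3 | 32 | 4 |
| (1,2) | 1-3 | 72 | 18 |
| (2,1) | 1-3 | 72 | 18 |
| (2,2) | 0-3 | 144 | 54 |
| (3,1) | 0-3 | 128 | 48 |
| (3,2) | 0-3 | 192 | 72 |
| Total | 20 baselines, 960 pairs | 640 | 214 |

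No pair disagrees the other way. These are counts of possible patterns, not expected frequencies.

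**3. The plan's own power figures**

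Inputs from protocol 12.4.2 and 12.8.1: rates of 35% v 20% (endpoint A, fibrosis) and 25% v 10% (endpoint B, resolution), correlation 0.5, two-sided alpha 0.05/2 = 0.025 per endpoint, 100,000 simulations, z-test without continuity correction. The statistic is z = (pC - pP) / sqrt[pC(1-pC)/nC + pP(1-pP)/nP].

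- 95 per arm: A 0.549, B 0.718, at least one 0.802. The protocol states 0.55, 0.72 and 0.80.
- 140 v 80: at least one 0.848. The protocol states 0.85.

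The figures reproduce with unpooled variance (pooled gives 0.789 and 0.799 for at least one).

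**4. Illustration of size**

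The documents give no rate of steatosis-grade increase. Assume a share fC of combination and fP of placebo SAP-rule responders have one, and take 35% and 20% as SAP-rule rates. Protocol-rule rates are then 35%(1-fC) and 20%(1-fP). Sample sizes are 140 v 80.

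| fC / fP (assumed) | Rates | Difference, points | Odds ratio | Power A | At least one |
|---|---|---|---|---|---|
| 0 / 0 | 35.0% v 20.0% | 15.0 | 2.154 | 0.61 | 0.85 |
| 10% / 10% | 31.5% v 18.0% | 13.5 | 2.095 | 0.54 | 0.83 |
| 20% / 20% | 28.0% v 16.0% | 12.0 | 2.042 | 0.48 | 0.82 |
| 0 / 10% | 35.0% v 18.0% | 17.0 | 2.453 | 0.74 | 0.88 |
| 0 / 20% | 35.0% v 16.0% | 19.0 | 2.827 | 0.85 | 0.92 |

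With fP of 5-15% and fC of 0-5%, placebo is 17.0-19.0% and combination 33.25-35.0%. The difference runs from 33.25 - 19.0 = 14.25 to 35.0 - 17.0 = 18.0 points.

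The difference is unchanged when 35fC = 20fP, that is fP = 1.75fC. The protocol rule widens it only if the placebo share exceeds 1.75 times the combination share.

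The protocol does not say which rule the 35% and 20% assume. If they are protocol-rule rates, the SAP rule raises them: placebo to 20/0.95 = 21.1% up to 20/0.85 = 23.5%, combination to between 35.0% and 35/0.95 = 36.8%. The SAP-rule difference is then 35.0 - 23.5 = 11.5 to 36.8 - 21.1 = 15.7 points, against 15.

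**The case against.** The strongest reply is that this is an old SAP and not a live conflict. It predates both amendments and cannot run the current primary analysis: it has no placebo comparison, a composite primary endpoint and one-sided 0.05 tests. The sponsor recognised the change in definition and assigned it to the SAP. Protocol 12.4.1 is itself explicit. All of that stands, and it explains how the mismatch arose. It does not remove it, because no updated definition is in the documents. An update that rebuilt the arms, endpoints and alpha could still carry the appendix derivation over unchanged.

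A second reply is that the primary estimand named in SAP 5.3.11.2 is the old composite, not today's first primary endpoint. That is correct. In this SAP the present first primary endpoint is a key secondary, but Table 2-4 attaches the same restriction to it: "no worsening of hepatocellular ballooning or lobular inflammation) at Week 48 compared with baseline".

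A third reply concerns bias. A reader might infer that the SAP rule shifts the treatment effect in a known direction, because both drugs lower liver fat (protocol 1.1.3 and 1.1.4). The documents support that as plausible only. They give no rate of steatosis increase by arm, and none among participants whose fibrosis improved. Any difference between arms in the illustration comes from the assumed shares.

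**Conclusion.** The mismatch is confirmed from current text in both documents. The SAP rule is strictly more lenient, and every disagreement turns a protocol non-responder into a SAP responder. It affects the first primary endpoint, the key secondary composite (where NASH resolution is not also met) and the two-stage fibrosis endpoint. The second primary endpoint is unaffected: both documents define resolution as inflammation of 1 or less with ballooning of 0.

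The size is unknown. Equal assumed shares barely move the odds ratio, unequal ones can move it more, and even the direction depends on the shares. The stated power reproduces, and its calculation takes response rates as given, so it contains no error from this source.

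A reader might also infer that the trial's primary analysis will be run on the two-component rule. The documents do not show that, since this SAP needs revision before it could be used for that analysis. What they show is that the one place meant to hold the corrected definition still holds a different one. That is enough to require correction before unblinding, whatever the size.

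**What to change.** When the SAP is updated to the amended protocol, and before unblinding:

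- Replace SAP 5.3.11.2 with the protocol 12.4.1 rule: an increase in any one of steatosis, lobular inflammation or ballooning.
- Reword its reference to the primary estimand so that it names every endpoint the rule serves.
- Remove the two-component wording from SAP 1.2, 2.5 (including 2.5.1), 2.6 (2.6.1 and 2.6.2) and 2.7 (2.7.1).

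The cost of this item is one derivation and a handful of wording changes, with no new data. It does not by itself make the 2019 SAP fit for the amended design. The arms, primary endpoints, hypotheses and alpha need the wider update in any case, and this definition should be a named item in it.
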